### **5.2.3 Guideline for Dose Modification and Treatment Discontinuation**

For individual subjects, dose delays and modifications of trial treatment will be based on treatment-related toxicity, laboratory test results prior to treatment administration, and clinical assessments during the previous cycle and on the day of treatment. Guidelines for dose delay and dose modification for Parts 1 and 2 are described below and are applicable to the start of each cycle as well as during the cycle if treatment-related toxicities occur.

#### **5.2.3.1 Preladenant Dose Modifications**

Adverse events (both non-serious and serious) associated with preladenant and pembrolizumab exposure may represent an immunologic etiology. These adverse events may occur shortly after the first dose or several months after the last dose of treatment.

The Common Terminology Criteria for Adverse Events, version 4.0 (CTCAE 4.0) must be used to grade the severity of adverse events. The investigator may attribute each toxicity event to preladenant alone, or to the combination of preladenant and pembrolizumab, and modify the dose according to [Table 7](#) and [Table 8](#) (*pembro dose mod table added to Section 5.2.3.2*). If a dose modification for toxicity occurs with preladenant, the dose may not be re-escalated to the dose which preceded the dose modification. Dose modifications are always based on the previous cycle.

Reduction or holding of one agent and not the other agent is appropriate if, in the opinion of the investigator, the toxicity is clearly related to one of the study drugs. For example, in the combination arm (Arm 2), if preladenant is held due to an adverse event attributed to that drug, then pembrolizumab may continue to be administered. Appropriate documentation is required regarding which drug the investigator is attributing the adverse event to. If, in the opinion of the investigator, the toxicity is related to the combination of two agents, then both drugs should be held according to recommended dose modifications.

Subjects may have up to 2 dose modifications of preladenant throughout the course of the study, as described in Table 7. If further toxicity occurs or the criteria for resuming treatment are not met, the subject must be discontinued from the agent. If a subject experiences several toxicities and there are conflicting recommendations, follow the most conservative dose adjustment recommended (dose reduction appropriate to the most severe toxicity).

Exceptional circumstances to following the dose modification tables below may be considered after consultation with the Sponsor.

**Table 7 Preladenant Dose Modification and Treatment Discontinuation Guidelines for Drug-Related Adverse Events**

Toxicity	Hold Treatment	Criteria for Restarting Treatment	Dose/Schedule for Restarting Treatment	Criteria for Discontinuation after Consultation with Sponsor
Hematological toxicities:				
• Any Grade 1 hematological toxicity	No	N/A	N/A	N/A
• Any Grade 2 hematological toxicity, or Grade 3 toxicity that persists for ≤ 5 days	Per medical assessment of the Investigator	If treatment held, may be restarted when AE resolves back to baseline or to Grade 1.	Per medical assessment of the investigator: may decrease dose by one dose level.	If AE persists for 12 weeks without resolution following reduction in dose.
• Any Grade 3 hematologic toxicity that persists for > 5 days, or Grade 4 hematological toxicity • Febrile neutropenia • Grade 3 thrombocytopenia of any durations if associated with bleeding	Yes	Treatment may be restarted when AE resolves back to baseline or to Grade 1.	Decrease dose by one dose level.	If AE persists for 12 weeks without resolution following reduction in dosing schedule.  Permanent discontinuation should be considered for any severe or life-threatening event
Non-hematological toxicities:				
• Toxicity	Hold Treatment	Criteria for Restarting Treatment	Dose/Schedule for Restarting Treatment	Criteria for Discontinuation after Consultation with Sponsor
• Any Grade 1 non-hematological toxicity • Grade 2 alopecia • Grade 2 fatigue	No	N/A	N/A	N/A
• Any Grade 2 non-hematological toxicity except Grade 2 alopecia and Grade 2 fatigue	Per medical assessment of the investigator	If treatment held, may be restarted when AE resolves back to baseline or to Grade 1.	Per medical assessment of the Investigator: may decrease dose by one dose level.	If AE persists for 12 weeks without resolution following reduction in dose.

Toxicity	Hold Treatment	Criteria for Restarting Treatment	Dose/Schedule for Restarting Treatment	Criteria for Discontinuation after Consultation with Sponsor

 
Any Grade 3 or 4 non-hematological toxicity (not including laboratory, unless clinically significant medical intervention is required to treat the subject, or the abnormality leads to hospitalization, or the abnormality persists for >1 week)
 
	Yes	Treatment may be restarted when AE resolves back to baseline or to Grade 1.	Decrease dose by one dose level.	If AE persists for 12 weeks without resolution following reduction in dose. Permanent discontinuation should be considered for any severe or life-threatening event

In case toxicity does not resolve to Grade 0-1 within 12 weeks after last treatment, preladenant should be discontinued after consultation with the Sponsor.

With Investigator and Sponsor agreement, subjects with a laboratory adverse event still at Grade 2 after 12 weeks may continue treatment in the trial only if asymptomatic and controlled.

After any Grade 4 drug-related adverse event, subjects should not restart study treatment without consultation with the Sponsor. (Toxicity must have resolved to 0-1 or baseline prior to restarting).

Dose reductions are not permitted during Cycle 1.

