### 5.2.1.4 Tolerability Evaluation Rules and Dose Escalation

Four dose levels of preladenant are planned in Part 1 ([Table 5](#) and [Table 6](#))

The starting dose (DL1) of preladenant is 25 mg BID. Dose escalation will continue as outlined above (Section 5.2.1.2) according to mTPI dose finding rules.

Table 5 Dose Levels for Preladenant Monotherapy (Part 1: Arm 1)

Arm 1	Preladenant (BID)	
	mg per dose	mg per day
DL-1	10	20
DL1	25	50
DL2	50	100
DL3	100	200
DL4	200	400

Table 6 Dose Levels for Preladenant and Pembrolizumab (Part 1: Arm 2)

Arm 2	Preladenant (BID)		Pembrolizumab (Q3W)
Dose Levels	mg per dose	mg per day	IV Infusion (mg per dose)
DL-1	10	20	200
DL1	25	50	200
DL2	50	100	200
DL3	100	200	200
DL4	200	400	200

Each individual subject will be assigned to a single dose level of study therapy. Intra-subject dose escalation is not allowed. Individual patient dose interruptions and/or dose decreases for preladenant may be implemented based on toxicity as described in Section 5.2.3.1. However, dose adjustments should not be made during the DLT observation period without discussion with the Sponsor. In Arm 2, pembrolizumab administration can be delayed or interrupted but will not be de-escalated see Section 5.2.3.2.

The decision to enroll subjects in the next dose level will be made by the sponsor in consultation with the participating investigators after reviewing the safety and any available PK data of the previous dose level(s).

Subjects may continue on treatment until disease progression, unacceptable toxicity, investigator's decision to withdraw the subject, withdrawal of consent, development of an inter-current condition precluding further administration of study treatment, pregnancy of the subject, failure to comply with dosing evaluations or other study requirements, or administrative reasons requiring cessation of treatment, at which point they will be discontinued from the study.

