### **5.2.2 Definition of Dose-Limiting Toxicities**

All toxicities will be graded using NCI CTCAE Version 4.0 based on Investigator assessment (Appendix 12.5).

The DLT window of observation will be during Cycle 1 (Day 1 to Day 21).

The occurrence of any of the following toxicities during Cycle 1 will be considered a DLT, if assessed by the Investigator to be possibly, probably or definitely related to study drug administration:

- 1) Grade 4 non-hematologic toxicity (not laboratory).
- 2) Grade 4 hematologic toxicity lasting  $\geq 7$  days, except thrombocytopenia
  - a) Grade 4 thrombocytopenia of any duration
  - b) Grade 3 thrombocytopenia associated with bleeding
- 3) Grade 3 non-hematologic toxicity (not laboratory) lasting  $>3$  days despite optimal supportive care.

- 4) Any Grade 3 or Grade 4 non-hematologic laboratory value if:
  - Medical intervention is required to treat the subject, or
  - The abnormality leads to hospitalization, or
  - The abnormality persists for >72 hours.
  - Exceptions:
    - Clinically non-significant, treatable, or reversible laboratory abnormalities including uric acid, etc.
- 5) Any of the following liver test abnormalities are observed (Hy's Law)
  - ALT or AST > 3X ULN **with** TBL > 2X ULN with no elevation in alkaline phosphatase (AP < 2X ULN)
  - No other reasons can be found to explain the combination of increased AT and TBL, such as viral hepatitis, A,B or C, preexisting or acute liver diseases, or another drug capable of causing the observed injury
- 6) Febrile neutropenia Grade 3 or Grade 4:
  - Grade 3 is defined as ANC <1000/mm^3 with a single temperature of >38.3 degrees C (101 degrees F) or a sustained temperature of ≥38 degrees C (100.4 degrees F) for more than one hour
  - Grade 4 is defined as ANC <1000/mm^3 with a single temperature of >38.3 degrees C (101 degrees F) or a sustained temperature of ≥38 degrees C (100.4 degrees F) for more than one hour, with life-threatening consequences and urgent intervention indicated.
- 7) Prolonged delay (>2 weeks) in initiating cycle 2 due to treatment-related toxicity.
- 8) Any treatment-related toxicity which causes the subject to discontinue treatment during Cycle 1.
- 9) Missing >25% of Preladenant doses as a result of drug-related AE(s) during the first cycle.
- 10) Grade 5 toxicity.

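### Cycle 1 preladenant reductions are banned in one place and left open in others; if one is made without a DLT, the counting rules treat the subject as DLT-free at the assigned dose

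*Combined protocol and SAP*

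**What the plan says.** Four statements govern preladenant dose changes in Cycle 1, which Section 5.2.2 also makes the DLT window (Days 1 to 21).

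- Section 5.2.3.1, notes under Table 7: "Dose reductions are not permitted during Cycle 1".
- Section 5.2.1.4: "Individual patient dose interruptions and/or dose decreases for preladenant may be implemented based on toxicity as described in Section 5.2.3.1". The next sentence adds that "dose adjustments should not be made during the DLT observation period without discussion with the Sponsor".
- Section 5.2.3.1, text before Table 7: "Exceptional circumstances to following the dose modification tables below may be considered after consultation with the Sponsor". The same section ties modifications to the preceding cycle.
- Section 5.2.3: the guidelines "are applicable to the start of each cycle as well as during the cycle if treatment-related toxicities occur".

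Three places decide how a subject is counted.

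- Section 5.2.2: the only DLT criterion that refers to preladenant intake is criterion 9, "Missing >25% of Preladenant doses as a result of drug-related AE(s) during the first cycle". None of the ten criteria names a dose reduction.
- Section 5.2.2.1: a subject who received 75% or less of the preladenant doses is replaced, but only if there was no drug-related AE. Section 5.9 repeats the replacement rules without this one. Neither section mentions a reduction.
- Section 8.5.1: the DLT set needs 21 days of safety observation after the first dose of assigned treatment, or a DLT. Analysis by treatment actually received is specified for administration errors only.

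**The concern.** A site reading Table 7 would conclude that a Cycle 1 reduction is not available. A site reading Section 5.2.1.4, or the exceptions sentence in Section 5.2.3.1, could conclude that it is available after a call to the Sponsor.

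If a reduction is made by that route, the subject has not been on the assigned dose for the whole DLT window. The counting rules look at DLTs, missed doses and days of observation, not at the dose level taken. Such a subject can therefore add one to the Table 4 denominator and nothing to the numerator at a dose that was stopped part-way. Under the plan's own assumption that DLT risk does not fall with dose (Section 5.2.1.2), this pushes the DLT rate at that level down. The same counts feed the pooled DLT estimates (Sections 5.2.1.2 and 8.6.2), the preliminary RP2D, and so the dose given to about 60 Part 2 subjects.

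**Working it through.** **1. Do the rules conflict?** All four statements apply to the same 21 days. Table 7's note has no exception in its own sentence. Section 5.2.1.4 names decreases and interruptions together, then restricts adjustments by a condition (Sponsor discussion) rather than a ban. Taken alone it leaves a decrease possible. Section 5.2.3.1 offers a second route through its exceptions sentence. In the other direction, Section 5.2.1.4 defers to Section 5.2.3.1, which contains the ban, and a rule based on the preceding cycle has nothing to act on in Cycle 1. Section 5.2.3 applies the guidelines within a cycle, which pulls back again. The text supports both readings.

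**2. Which reduced subjects escape the counting rules?** Planned intake is 2 × 21 = 42 doses, and 25% of 42 is 10.5. Missing 11 doses (11/42 = 26.2%) for a drug-related AE is a DLT under criterion 9; missing 10 (10/42 = 23.8%) is not. In Table 7 a decrease comes at restart, normally after a hold, so the hold must be at most 10 doses and the restart must fall inside Cycle 1.

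The toxicity must also not be a DLT in itself. Such cases exist. Table 7 calls for a hold and a one-level decrease after Grade 3 non-hematologic toxicity, whereas criterion 3 makes the non-laboratory kind a DLT only beyond 3 days. Grade 3 neutropenia without fever lasting more than 5 days also triggers a hold and decrease without being a listed DLT.

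Worked case: a Grade 3 non-laboratory event starts on Day 8 and resolves in 3 days. Six doses are held, and treatment restarts on Day 11 one level lower.

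- Missed: 6/42 = 14.3%, so criterion 9 is not met on a count of doses.
- Received: 36/42 = 85.7%, so the 75% replacement rule is not met. It would not apply anyway, because there was a drug-related AE.
- Observed for 21 days, so the subject is in the Section 8.5.1 DLT set.

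Result: evaluable, no DLT, at the assigned dose.

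**3. How much drug was taken?** Fraction of intended mg = (F + r × L)/42, where F is doses at the assigned level, L is doses at the lower level, and r is 0.5 (200 to 100, 100 to 50, 50 to 25 mg) or 0.4 (25 to 10 mg).

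| Case | F | L | r = 0.5 | r = 0.4 |
|---|---|---|---|---|
| Reduced from Day 8, none missed | 14 | 28 | 28/42 = 66.7% | 25.2/42 = 60.0% |
| Worked case above | 14 | 22 | 25/42 = 59.5% | 22.8/42 = 54.3% |

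**4. What if doses in criterion 9 means milligrams?** The plan does not define this. With no missed doses, a halving from Day 11 leaves 31/42 = 73.8% and would cross the limit; from Day 12 it leaves 32/42 = 76.2% and would not. For 25 to 10 mg the change falls between Day 13 (31.2/42 = 74.3%) and Day 14 (32.4/42 = 77.1%). On this reading early reductions for a drug-related AE, including the worked case, would be DLTs. Later ones escape on either reading.

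**5. Can one subject change the decision?** Table 4 was reproduced first: Beta(1 + x, 1 + n − x) posterior, target 30%, intervals (0, 0.27), (0.27, 0.33) and (0.33, 1), largest probability per unit length wins. DU was taken as P(rate > 0.30) above 0.95, an assumption because the plan states no cutoff. All 78 legible cells in rows 0 to 6 match.

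- 0/3: 0.716/0.27 = 2.65; 0.0825/0.06 = 1.37; 0.2015/0.67 = 0.30. Escalate.
- 1/3: 0.296/0.27 = 1.10; 0.1056/0.06 = 1.76; 0.5985/0.67 = 0.89. Stay.

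Likewise 1/6 is escalate and 2/6 is stay. If a reduced subject in a 0/3 cohort were replaced, a DLT in the replacement would give 1/3 (stay) and no DLT would leave 0/3 (escalate).

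**The case against.** The strongest reply is that the rules can be followed together. Section 5.2.1.4 permits changes only as Section 5.2.3.1 describes, and that section forbids Cycle 1 reductions. Its Sponsor-discussion sentence is a restriction, and would then cover only what remains, namely interruptions. This reading is tenable. A reader might infer that Section 5.2.1.4 cannot be confined to interruptions; given the cross-reference, that is too strong. But it names decreases immediately beforehand, and the exceptions sentence in Section 5.2.3.1 is a separate opening, so the text does not close the question.

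Second, the miscount needs a chain: an exception to the ban, a toxicity short of a DLT, a short hold, and a lower-dose restart within the same 21 days. That stands. It limits how often the problem could occur, and the documents give no frequency.

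Third, the Sponsor would know of each case, reviews safety and PK data before opening the next level (Section 5.2.1.4), and weighs all the data for the RP2D (Section 5.2.1.2). This is a partial safeguard. It does not correct the count, and Section 5.2.1.2 bases escalation decisions on DLT occurrence.

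Finally, a reader might infer that such a cohort holds only two fully dosed subjects and so breaches the minimum of three. Section 5.2.1.2 asks for three subjects, not three fully dosed ones, and Section 5.2.2.1 accepts incomplete intake. That argument is not supported.

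**Conclusion.** The point holds conditionally. The plan does not settle whether a Cycle 1 preladenant reduction is ever possible. If one is made under the conditions in step 2, the stated rules enter the subject in Table 4 as DLT-free at a dose not received throughout, which can bias that level's count down. If the Table 7 ban is followed strictly, nothing is miscounted.

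On size, the daily dose falls by 50% (60% from 25 to 10 mg) only from the day of reduction. A reader might take that as the loss over the whole window, but a Day 8 reduction with no missed doses leaves about 60% to 67% of intended milligrams. One subject's status can decide between escalate and stay. It would be wrong to infer that the decision should have been stay: that requires the event to be a DLT, which the plan does not say.

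The conclusion assumes that criterion 9 counts doses taken; on a milligram reading only the later reductions escape. No probability of a wrong escalation is given, because the documents supply neither the frequency of such reductions nor the DLTs they might avert.

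**What to change.** Reconcile the Table 7 note, the exceptions and preceding-cycle sentences in Section 5.2.3.1, the within-cycle wording of Section 5.2.3, and Section 5.2.1.4, so that one rule on Cycle 1 reductions is stated. Which clinical rule it should be is for the sponsor; no view is taken here.

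If any exception is kept, or a deviation occurs, state in Sections 5.2.2.1 and 8.5.1 that a subject whose preladenant was reduced in Cycle 1 without a DLT is not counted in Table 4 as DLT-free at the assigned dose. Align Section 5.9 with this. Leave the DLT definition in Section 5.2.2 unchanged, since a DLT also carries consequences for continued treatment (Section 5.2.2.1).

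The cost is protocol wording and an occasional replacement subject, with the wait for that subject's 21 days.

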### 5.2.4 Timing of Dose Administration

All trial treatments will be administered on an outpatient basis.

Trial treatment should be administered after all procedures/assessments have been completed as detailed on the Trial Flow Chart (Section 6.0).

Table 9 Treatment Schedule for Preladenant Monotherapy in each Arm for each Treatment Cycle

Treatment Arm 1 (Part 1)	Day 1		Days 2 – 21	
	am	pm	am	pm
Preladenant	X*	X	X	X
* The AM dose of preladenant on Day 1 of each cycle is witnessed at the site.				

Table 10 Treatment Schedule for Preladenant and Pembrolizumab in each Arm for each Treatment Cycle

Treatment Arm 2 (Part 1 and Part 2)	Day 1		Days 2 – 21	
	am	pm	am	pm
Preladenant	X*	X	X	X
Pembrolizumab	X			
* The AM dose of preladenant on Day 1 of each cycle is witnessed at the site.				

During the study (in Part 1 and Part 2, and in Arm 1 and Arm 2), starting on Day 1 of Cycle 1, preladenant will be administered orally BID (twice a day) approximately every 12 hours on each day of a 21-day treatment cycle. Preladenant may be administered up to 4 hours before or after the scheduled time for preladenant oral intake. All capsules comprising a dose should be taken within approximately 15 minutes (See Pharmacy Manual).

In Arm 2 (Part 1 and Part 2), on Day 1 of each 21-day cycle, after preladenant administration in the morning, pembrolizumab will be administered at a fixed dose of 200 mg as a 30-minute IV infusion.

Sites should make every effort to target the pembrolizumab infusion timing to be as close to 30 minutes as possible. However, given the variability of infusion pumps from site to site, a window of -5 minutes and +10 minutes is permitted (i.e., infusion time is 30 minutes: -5 min/+10 min) (See Pharmacy Manual).

Trial treatment of pembrolizumab may be administered up to three days before or after the scheduled Day 1 of each cycle due to administrative reasons (up to three days after treatment allocation is permitted).

The Pharmacy Manual contains specific instructions for the handling of preladenant and for the preparation of the pembrolizumab infusion fluid and administration of infusion solution.

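### In Cycle 1 the mandatory-hold rows of Table 7 leave no permitted restart dose, so the same short toxicity may or may not be scored as a DLT under criterion 9

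*Combined protocol and SAP*

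**What the plan says.** **Holding and restarting (Section 5.2.3.1, Table 7).** A hold is mandatory for drug-related Grade 3 or 4 non-hematologic toxicity, with no minimum duration for non-laboratory events. It is also mandatory for "Any Grade 3 hematologic toxicity that persists for > 5 days, or Grade 4 hematological toxicity", for febrile neutropenia and for Grade 3 thrombocytopenia with bleeding. Restart is possible once the event is back to baseline or Grade 1, and the restart entry in these rows is "Decrease dose by one dose level". In the rows for Grade 2 toxicity and for Grade 3 hematologic toxicity of 5 days or less, both the hold and the reduction are optional. The note below the table says "Dose reductions are not permitted during Cycle 1".

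**Related text.** Section 5.2.3 applies the guidelines within a cycle as well as at its start. Section 5.2.3.1 ties modifications to the preceding cycle and allows exceptions to the tables after Sponsor consultation. Section 5.2.1.4 contemplates dose adjustments in the DLT period if first discussed with the Sponsor.

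**Scoring (Section 5.2.2).** Criterion 2 counts Grade 4 hematologic toxicity, other than thrombocytopenia, only from 7 days. Criterion 3 counts Grade 3 non-laboratory, non-hematologic toxicity only beyond 3 days. Criterion 9 is "Missing >25% of Preladenant doses as a result of drug-related AE(s) during the first cycle".

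**The concern.** After a mandatory hold resolves within Cycle 1, restarting at the assigned dose departs from Table 7, and restarting one level down departs from the note. Taken literally, the two instructions keep the subject off drug until Cycle 2. The missed doses can be attributed to a drug-related event, so criterion 9 may score as a DLT an event that criterion 2 or 3 leaves out because it was brief. A site that restarts at the assigned dose would record the same event as no DLT.

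The DLT rate is the primary safety endpoint (Sections 4.2.3.1 and 8.4.2), and Section 5.2.1.2 bases escalation and de-escalation on it through Table 4. With cohorts as small as 3 subjects, one reclassified subject changes the decision: 0 of 3 is escalate, 1 of 3 is stay, 2 of 3 is de-escalate.

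**Working it through.** **1. The plan's own figures.** The documents give no figure for the hold-and-restart rule. The rule that uses the DLT count, Table 4, does reproduce. With a 30% target, a Beta(1,1) prior, both epsilons at 0.03 and an unacceptable-toxicity cut-off of 0.95 (assumed; the documents do not state it), all 78 legible cells in rows 0 to 6 match. Rows 7 and 8 are broken in the text and were not compared.

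**2. Doses in Cycle 1.** Section 5.2.4: "preladenant will be administered orally BID (twice a day) approximately every 12 hours on each day of a 21-day treatment cycle". So 2 × 21 = 42 doses.

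**3. Criterion 9 threshold.** 25% of 42 = 10.5, so 11 or more missed doses is a DLT.

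**4. Two ways of handling the same hold** (arithmetic only, not a preference):

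| Handling | Missed doses | Share of 42 | Criterion 9 |
|---|---|---|---|
| Same-dose restart, 3-day hold | 6 | 14.3% | no |
| Same-dose restart, 5-day hold | 10 | 23.8% | no |
| Same-dose restart, 5.5-day hold | 11 | 26.2% | DLT |
| No restart, hold from Day 16 morning | 12 | 28.6% | DLT |
| No restart, hold from Day 16 evening | 11 | 26.2% | DLT |
| No restart, hold from Day 17 morning | 10 | 23.8% | no |

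Without a restart, a hold beginning with the morning dose of Day d misses 2 × (22 − d) doses. Of the 42 possible starting doses, 32 (76%) lead to a DLT, however quickly the event resolves.

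**5. Events whose score depends on the conflict.**
- *Mainly:* Grade 3 non-hematologic, non-laboratory events of 3 days or less that return to Grade 1 or baseline soon enough for the hold to last 5 days or less, with the hold starting by Day 16 evening.
- *Also:* some Grade 4 non-platelet hematologic events under 7 days with similarly short holds, and Grade 3 hematologic events over 5 days.
- *Not affected:* Grade 4 non-hematologic non-laboratory events (criterion 1), Grade 4 thrombocytopenia and Grade 3 thrombocytopenia with bleeding (criterion 2), and febrile neutropenia (criterion 6). These are DLTs already.

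**6. A separate overlap.** A Grade 4 hematologic hold of 5.5 days or more meets criterion 9 (11 of 42) whatever the restart rule, although criterion 2 asks for 7 days at Grade 4. The hold runs until Grade 1 or baseline, so it can outlast the time spent at Grade 4.

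**7. Illustration with assumed rates.** Let b be the DLT rate from all other causes and s the rate of short excluded events, with onset uniform over the cycle and no restart. The scored rate is p = b + (1 − b) × s × 32/42. With 3 subjects, the chance of escalating is (1 − p)³.
- b = 10%, s from 5% to 20%: p = 13.4% to 23.7%. The chance of escalating falls from 0.729 to between 0.649 and 0.444.
- b = 20%, s from 5% to 20%: p = 23.0% to 32.2%. The chance falls from 0.512 to between 0.456 and 0.312.

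Neither b nor s comes from the documents.

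**The case against.** The case on the other side is substantial. The optional-hold rows permit a same-dose restart, and many mandatory-hold events are DLTs anyway. The note can be read as a specific Cycle 1 exception to a general restart column. The sentence tying modifications to the preceding cycle supports that reading, since Cycle 1 has none. Sponsor involvement is provided for: discussion under Section 5.2.1.4, exceptions under Section 5.2.3.1, consultation before any restart after a Grade 4 drug-related event, and joint escalation decisions under Section 5.2.1.2. Finally, the background describes preladenant as generally well tolerated, with asymptomatic enzyme rises and mild, transient blood pressure increases, so short non-laboratory Grade 3 events may be uncommon.

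The limits on scope stand, and so does the point that the rates are unknown. The escape routes do not remove the conflict. Section 5.2.1.4 itself disagrees with the flat bar in the note, and Section 5.2.3 applies the table within a cycle. The exceptions clause works case by case and is silent on scoring. The consultation required before restart is written for Grade 4, not for the Grade 3 non-hematologic events where the score is most exposed.

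A reader might infer that every subject held in Cycle 1 becomes a DLT, or that the RP2D is biased low. The documents support neither. Holds from Day 17 onward stay below 25%, and the literal reading is only one of those available. Section 5.2.1.2 treats the dose closest to 30% as preliminary, to be weighed with the totality of the data. Section 2.1 adds late toxicities, PK, PD and preliminary efficacy before the RP2D is final.

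**Conclusion.** The inconsistency is real and narrow. In the mandatory-hold rows, Table 7 and its Cycle 1 note together leave no permitted restart dose. If both are followed, a hold starting by the evening dose of Day 16 is a DLT under criterion 9 (at least 26% of doses missed), whereas a 3-day hold with a same-dose restart is not (14%). It matters chiefly for the brief Grade 3 non-hematologic events that criterion 3 leaves out. Criteria 2 and 9 also overlap for Grade 4 hematologic holds of 5.5 days or more, with or without the restart conflict.

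The consequence is inconsistent scoring of the primary endpoint. The dose counts assume the full 42-dose schedule and a continuous hold. The size of the effect on the DLT rate or on escalation cannot be stated; the illustration shows only direction and sensitivity.

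**What to change.** 1. The clinical team should reconcile Table 7's restart column, its Cycle 1 note and the statements in Sections 5.2.1.4, 5.2.3 and 5.2.3.1, so that a subject held in Cycle 1 has one permitted path.
2. Section 5.2.2 should reconcile criterion 9 with the duration limits in criteria 2 and 3, and state whether doses withheld after the event has resolved count as missed.
3. Sections 5.2.2.1, 5.9 and 8.5.1 should be aligned with the result. At present, taking 75% or less of 42 doses (31 or fewer) is the same line as missing 11 or more. Section 5.2.2.1 replaces such a subject only if there was no drug-related event, Section 5.9 has no preladenant-dose ground for replacement, and Section 8.5.1 treats any treated subject observed for 21 days as evaluable. A change to criterion 9 alone could leave a subject's status undefined or inconsistent.

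Which clinical rule is right is for that team; no dose, DLT rule or replacement rule is proposed here. The cost is amendment wording in these sections, and the reconciliation does not in itself require more subjects or a change to Table 4.
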